7.5. Other Safety Measures

Eastern Cooperative Oncology Group (ECOG) performance status is an investigator assessment of the impact of the disease on the subject's activities of daily living. ECOG assessments will be performed at the time points listed in the Study Procedures Table (Appendix 2 of the protocol).

By-subject listings will be generated for the All Enrolled Analysis Set by treatment arms and subject ID number in ascending order for the following safety parameters and comments:

- ECOG performance scores
- General Comments

7.6. Changes from Protocol-Specified Safety Analyses

Protocol defined a secondary endpoint of Time to onset of AEs of interest (AEIs). This analysis was not performed.

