	
The Safety Analysis Set will include data from all subjects who receive at least 1 dose of study treatment, with treatment assignments designated according to the actual treatment received. This analysis set will be used in the analyses of safety variables as well as study treatment administration.
 
The PK Analysis Set will include data from subjects in the Safety Analysis Set who have received the study drug and have at least 1 sample with detectable drug concentration.
 
An IRC will review radiographic data and pertinent clinical data in order to provide expert evaluation of tumor status, without receiving treatment assignment. The findings of the IRC will be considered primary for analyses of the primary efficacy endpoint and other tumor control endpoints. Tumor response status and progression will be assessed by the IRC using standard response criteria.
 
Efficacy Analysis
 
For the primary efficacy analysis, ORR will be evaluated by treatment arm using the IRC assessments in the ITT Analysis Set. Subjects who do not have sufficient baseline or on-study tumor assessment to characterize response will be counted as non-responders. Estimates and the corresponding 95% CIs based on the Clopper-Pearson exact method will be provided. The potential impact of subject baseline characteristics on treatment response may be explored with logistic regression modeling.
 
The time-to-event efficacy endpoints including PFS, DOR, and OS will be analyzed using the Kaplan-Meier method in the ITT Analysis Set, and the analyses of DOR will include subjects who achieve a PR or CR.
 
Safety Analysis
 
Safety will be assessed via AEs, clinical laboratory tests, and concomitant medications. Information regarding study drug administration, study drug compliance, and other safety variables will be summarized by treatment arm.
 
For the primary safety endpoint, the number and percentage of subjects who experienced at least 1 \geq Grade 4 TEAE will be listed and summarized by treatment arm. The severity, timing, relationship to study drug, and drug interruptions for \geq Grade 4 TEAEs will be summarized.
 
The frequency, severity, timing, and drug interruptions for AEs will be summarized by treatment arm using descriptive statistics. Time to onset and resolution of AEI will be analyzed using the Kaplan-Meier method.

--	--

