8.6.2. Adverse Events

All AEs will be listed. The focus of AE summarization will be on treatment-emergent AEs. A treatment-emergent AE is defined as any AE with onset date on or after the date of first dose of study drug up to 30 days after permanent study drug discontinuation or any AEs leading to premature study drug discontinuation.

AEs will be classified using Medical Dictionary for Regulatory Activities with descriptions by system organ class (SOC), high-level group term, high-level term, preferred term (PT), and lower-level term. The severity of AEs will be graded by the investigator according to the CTCAE, Version 5.0, whenever possible. If a CTCAE criterion does not exist for a specific type of AE, the grade corresponding to the appropriate adjective will be used by the investigator to describe the intensity of the AE: Grade 1 (mild), Grade 2 (moderate), Grade 3 (severe), Grade 4 (life threatening), or Grade 5 (fatal). The relationship of the AE to the study drug will be categorized as related or unrelated.

For the primary safety endpoint, the number and percentage of subjects who experienced at least one Grade ≥ 4 TEAE will be listed and summarized by SOC and PT, and by treatment arm in the Safety Analysis Set. The severity, timing, relationship to study drug, drug interruptions, reductions, and discontinuations for Grade ≥ 4 TEAEs will be summarized.

Summaries (number and percentage of subjects) of TEAEs by SOC and PT will be provided. A subject who reports multiple TEAEs within the same PT (or SOC) is counted only once for that PT (or SOC) using the worst severity grade. AE descriptions will be presented by decreasing frequency for a given SOC and PT.

Separate summaries will be prepared for the following types of TEAEs:

- Idelalisib-related AEs
- AEs that are Grade ≥ 4 in severity

- AEs that are Grade ≥ 3 in severity
- AEs leading to study drug interruption, reduction, or discontinuation
- SAEs

Additional analysis on AEs will be performed. The AEs include: Grade ≥ 3 diarrhea/colitis, rash, febrile neutropenia, infection, and any grade of the following: pneumonitis, bowel perforation, progressive multifocal leukoencephalopathy (PML), PJP, CMV infection, and organizing pneumonia. The frequency, severity, timing, and drug interruptions for AEs will be summarized by treatment arm using descriptive statistics. Time to first onset of AEs and time to resolution will be summarized using the Kaplan-Meier method.

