1.2.2. Secondary Endpoints

- DOR, defined as the interval from the first documentation of CR or PR to the earlier of the first documentation of disease progression by independent review committee (IRC or death from any cause
- ORR by Week 24, defined as the proportion of subjects who achieve a PR or CR by Week 24
- Overall safety profile of idelalisib, including the incidence of AEs and clinically significant laboratory abnormalities, severity, timing, and relationship to idelalisib of any AEs; SAEs; or AEs leading to interruption, reduction, or discontinuation of idelalisib Time to onset of AEs of interest (AEIs) defined as the interval from the start of idelalisib treatment to the first documentation of start of AEI
- PFS, defined as the interval from randomization to the earlier of the first documentation of disease progression by IRC or death from any cause
- OS, defined as the interval from randomization to death from any cause
- Idelalisib trough (predose) and peak (1.5-hour samples) plasma concentrations assessed by validated bioanalytical method

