7.1.6.1. Summaries of Adverse Events Incidence by Severity

The number and percentage of subjects who experienced at least 1 TEAE will be provided and summarized by SOC and PT.

The number and percentage of subjects who experienced at least 1 TEAE will be provided and summarized by PT and severity in descending order of total frequency:

- Treatment-Emergent Adverse Events by PT and Severity

For the AE categories described below, summaries will be provided by PT in descending order of total frequency:

- All Treatment-Emergent Adverse Events
- Grade 4 or Higher Treatment-Emergent Adverse Events
- Grade 3 or Higher Treatment-Emergent Adverse Events
- Treatment-Emergent Idelalisib related Adverse Events
- Treatment-Emergent Serious Adverse Events
- Treatment-Emergent Idelalisib related Serious Adverse Events
- Treatment-Emergent Adverse Events leading to discontinuation of Idelalisib
- Treatment-Emergent Adverse Events leading to temporary interruption of Idelalisib
- Treatment-Emergent Adverse Events leading to study discontinuation
- Treatment-Emergent Adverse Events leading to Death

A brief, high-level summary of AEs described above will be provided by treatment arms and by the number and percentage of subjects who experienced the above AEs.

For summaries of TEAEs by PT, multiple events will be counted only once per subject in each summary. Adverse events will be summarized and listed by PT in descending order of total frequency. For summaries by severity, the most severe severity will be used for those AEs that occurred more than once in a given subject during the study.

In addition, by-subject data listings will be provided by treatment arms and subject ID number in ascending order for the following:

- All AEs, indicating whether the event is treatment emergent
- All SAEs
- All Deaths
- All Adverse Events leading to Death
- All Adverse Events with Grade 3 or Higher
- All Adverse Events with Grade 4 or Higher

- All Adverse Events leading to discontinuation of Idelalisib
- All Adverse Events leading to temporary interruption of Idelalisib
- All Adverse Events leading to study discontinuation

A flag will be included in the listings to indicate whether the event is treatment emergent.

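### The SAP keeps time to onset of AEs of interest as a secondary endpoint but drops its analysis without a reason, and omits the protocol's other AEI and timing summaries without saying so

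*SAP*

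**What the plan says.** SAP 1.2.2 carries the endpoint over from the protocol: "Time to onset of AEs of interest (AEIs) defined as the interval from the start of idelalisib treatment", running to the first documented start of an AEI. The safety-profile endpoint in the same section also covers "severity, timing, and relationship to idelalisib of any AEs". SAP 7.6, the section for changes from the protocol's safety analyses, has one entry: "Protocol defined a secondary endpoint of Time to onset of AEs of interest (AEIs). This analysis was not performed".

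The protocol planned more than that one analysis. Its synopsis says: "Time to onset and resolution of AEI will be analyzed using the Kaplan-Meier method". Protocol 8.6.2 names the AEIs: diarrhea/colitis, rash, febrile neutropenia and infection at Grade 3 or worse, and pneumonitis, bowel perforation, PML, PJP, CMV infection and organizing pneumonia at any grade. For this list it says "The frequency, severity, timing, and drug interruptions for AEs will be summarized by treatment arm using descriptive statistics", and then "Time to first onset of AEs and time to resolution will be summarized using the Kaplan-Meier method". It writes AEs in these sentences, but the context and the synopsis show that AEIs are meant. For the primary safety endpoint it begins "The severity, timing, relationship to study drug, drug interruptions, reductions, and discontinuations for Grade" and goes on to say that these features of Grade 4 or worse TEAEs will be summarized.

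SAP 7.1.6.1 replaces this with counts. All TEAEs are tabulated by SOC and PT, and by PT and severity. Then: "For the AE categories described below, summaries will be provided by PT in descending order of total frequency". Those categories include Grade 3 or worse, Grade 4 or worse, serious, related, and events leading to interruption or discontinuation. SAP section 1 gives the SAP precedence over the protocol where they differ.

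**The concern.** The SAP is inconsistent with itself: it names an endpoint in 1.2.2 that it declines to analyse in 7.6. It is also incomplete as a record of change, because the reader of 7.6 is told of one dropped analysis when several are gone.

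The stake is the safety half of the trial's question. Protocol 1.3 asks whether the alternative schedule can match the approved one on efficacy with less toxicity, and Protocol 1.4 expects Arm C's lower exposure to reduce the frequency and severity of TEAEs. Some of the toxicities appear months into treatment. Protocol 1.3 gives median onset of 5 months for Grade 3 or worse diarrhea/colitis and 4.8 months for pneumonitis, and 7.5.12 gives 7.1 months for Grade 3 or 4 diarrhea/colitis across idelalisib-treated patients. For such events, the percentage of subjects affected reflects how long subjects stayed on drug as well as the rate at which the events occur.

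Grouping is lost as well. A subject with both diarrhea and colitis appears in two PT rows, so PT rows cannot be added to give subjects with the grouped event.

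**Working it through.** **1. What the protocol planned against what the SAP provides**

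| Analysis by arm | Protocol | SAP | Recorded in SAP 7.6? |
|---|---|---|---|
| Kaplan-Meier time to first onset of AEIs | Synopsis, 8.6.2 | Dropped | Yes, without a reason |
| Kaplan-Meier time to resolution of AEIs | Synopsis, 8.6.2 | Absent | No |
| Grouped AEI frequency, severity, timing, interruptions | 8.6.2 | Absent | No |
| Timing of Grade 4 or worse TEAEs | 8.6.2 | Absent | No |
| TEAE counts by PT, severity and category | 8.6.2 | Kept, 7.1.6.1 | Not applicable |

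The SAP's remaining time-related safety summaries are duration of exposure (4.2) and deaths within or beyond 30 days of last dose (7.1.6.2). Neither describes when an adverse event starts or ends.

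**2. The plan's own figures**

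These were checked to see whether any depends on the dropped analysis.

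- Original design (Protocol 8.8, SAP 1.4): 15% against 5%, 120 per arm, two-sided 0.05, stated 73%. With pooled variance, the null SE is sqrt(2 × 0.10 × 0.90 / 120) = 0.0387 and the alternative SE is sqrt((0.15 × 0.85 + 0.05 × 0.95) / 120) = 0.0382. Then z = (0.10 − 1.96 × 0.0387) / 0.0382 = 0.63, and power is 73.6%.
- Chance of 60 or more responders out of 120 at a true ORR of 56%: exact binomial 92.1%, stated 92%.
- Clopper-Pearson half-widths at n = 120: 9.1 to 9.3 points for ORR of 40% to 60%, and 7.5 to 9.1 points for AE rates of 20% to 40%. All are within the stated 10.

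All reproduce, and none uses time to onset. Dropping the analysis changes no stated figure.

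**3. Expected events**

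The input is the 15% rate for Grade 3 or worse diarrhea/colitis from Protocol 8.8. It comes from prior idelalisib studies and was the assumed rate for 150 mg twice daily continuously; no rate is given for Arm C. Final arm sizes are not in the documents, so the range is an assumption.

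- Arm of 26 (approximate size of each arm when Arm B closed): 0.15 × 26 = 3.9, about 4.
- Arm of 120 (planned): 0.15 × 120 = 18.

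**4. Why crude percentages depend on time on drug**

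This is an illustration only. Assume a constant hazard that gives 15% by 12 months: h = −ln(0.85) / 12 = 0.01354 per month. The cumulative percentage is 1 − exp(−h × months):

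| Months observed | Percentage with event |
|---|---|
| 4 | 5.3% |
| 6 | 7.8% |
| 8 | 10.3% |
| 12 | 15.0% |

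Two arms with identical hazards, one observed for 6 months and the other for 12, would show 7.8% against 15.0%. Protocol 1.3 also quotes a continuing rate of 0.041 per person-year for this event. That gives 1 − exp(−0.041 × 0.5) = 2.0% at 6 months and 1 − exp(−0.041) = 4.0% at 12. The level is lower, but the ratio is again about two to one with no difference in risk.

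**The case against.** The strongest reply is that the onset omission is disclosed, under a heading meant for such changes, in a SAP for a trial terminated early for slow enrollment. The SAP's revision table says the endpoint sections were added for completeness, so 1.2.2 can be read as a restatement of the protocol that 7.6 then modifies. Frequency and severity by arm are kept, exposure is summarized by arm, and all AEs are listed chronologically within subject. With few subjects, Kaplan-Meier curves may say little.

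Much of this stands. Early termination is a plausible reason for a shorter analysis, though the SAP does not offer it as one. The exposure summary would show a difference in time on drug, but nothing relates event onset to it. The SOC table covers all TEAEs together; the Grade 3 or worse and Grade 4 or worse tables are by PT only, so Grade 3 or worse infection, for example, has no subject count by arm.

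Several stronger readings are tempting and are not supported:

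- A reader might infer that the sole time-based toxicity comparison was removed. It was not the sole one: time to resolution and timing summaries were also planned. Nor was a comparison planned: SAP 3.5 rules out formal testing, and the analysis was a descriptive summary by arm.
- A reader might infer selective reporting, especially from the past tense in 7.6. The dropped analysis is openly recorded, and nothing in the documents shows that results influenced the decision. What remains is an unexplained and incomplete list of changes.
- A reader might infer that Arm C was aimed at the AEIs or at delaying them. The protocol speaks of toxicity and TEAEs in general, and delay is not a stated aim. Nor do all AEIs start late: Protocol 1.3 gives a 2-month median for Grade 3 or worse rash.

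**Conclusion.** The point holds as an unexplained omission that is wider than the SAP records. Followed as written, the SAP gives no result for a listed secondary endpoint, no grouped AEI counts, no time to resolution and no timing summary for AEIs or for the primary safety events. Only the first of these is acknowledged in 7.6.

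Its size is best stated as missing analyses. No sample size, power or precision figure changes. The expected 4 to 18 Grade 3 or worse diarrhea/colitis events per arm rest on the 15% rate and on assumed arms of 26 to 120. The upper end should not be read as what was lost, since it requires full enrolment in a trial that stopped early, and it applies at most to a continuous 150 mg arm.

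The change should be made because the toxicity question is central to the trial and the remedy is cheap.

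**What to change.** Restore a descriptive summary by arm for the AEI list in Protocol 8.6.2:

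- n (%) of subjects with each grouped AEI, each subject counted once per group;
- Kaplan-Meier time from first dose to first onset, as the protocol specifies, with the censoring date stated and no formal test;
- where events are too few for a useful curve, a reduced form such as counts with individual onset times.

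In SAP 7.6, give the reason for any part of the onset analysis that stays out, and list the other omitted protocol analyses (time to resolution, timing of AEIs, timing of Grade 4 or worse TEAEs), each with its reason. Mark 1.2.2 to match. If the SAP can no longer be amended, record the same in the CSR, where SAP section 1 sends later changes.

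Competing-risk estimates or fixed landmark weeks would be reasonable additions, but they go beyond the protocol's method and are not needed to close this point.

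The cost is some SAP wording and a few tables. AE onset dates are already collected, and SAP 7.1.5.2 already has rules for incomplete ones. The downside is imprecise estimates after early termination, which the text should state.

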8. PHARMACOKINETIC ANALYSES

Plasma concentrations of idelalisib/GS-563117 will be listed and summarized by treatment arm and visit using descriptive statistics (eg, sample size, arithmetic mean, geometric mean, % coefficient of variation, StD, median, minimum, and maximum).

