	
Subjects enrolled as of Protocol Amendments 5 and 6:
 
Subjects will be assessed for FL disease status by continuous use of a single radiographic imaging method including PET-CT, CT, or MRI at screening and at Weeks 12, 24, 36, 48, 60, and 84 until IRC documented disease progression, and at the End of Treatment (EOT) visit (unless radiographic assessments were performed within the 4 weeks prior to the EOT visit). After Week 84, radiographic assessments are performed at the discretion of the investigator. Screening CT/PET-CT/MRI may be performed within 6 weeks prior to the first dose. Subsequent scans may be done within 1 week prior to the clinic visit.
 
Subjects enrolled prior to Protocol Amendment 5:
 
Subjects will be assessed for FL disease status by continuous use of a single radiographic imaging method including PET-CT, CT, or MRI at screening and at Weeks 8, 16, 24, 36, 48, 60, and 84 until IRC documented disease progression, and at the EOT visit (unless radiographic assessments were performed within the 4 weeks prior to the EOT visit). After Week 84, radiographic assessments are performed at the discretion of the investigator. Screening CT/PET-CT/MRI may be performed within 6 weeks prior to the first dose. Subsequent scans may be done within 1 week prior to the clinic visit.

Study Drug, Dose, and Mode of Administration:
	
 • Arm A: Idelalisib 150 mg will be taken twice daily orally starting on Day 1 and administered continuously. Dose reduction to 100 mg twice daily is available, if required. • Arm C: Idelalisib 150 mg will be taken twice daily orally starting on Day 1 and administered continuously for 21 days, followed by 7 days of no study drug, within each 28-day cycle. Dose reduction to 100 mg twice daily (21 days on-treatment, 7 days off-treatment) is available, if required. 
The original protocol for this study included an Arm B, which was closed to enrollment as of Protocol Amendment 5.
 
 • Arm B (closed to enrollment as of Protocol Amendment 5): Idelalisib 100 mg will be taken twice daily orally starting on Day 1 and administered continuously. Dose reductions are not available.

Criteria for Evaluation:	
Safety/Efficacy Primary Endpoints:	
 • ORR, defined as the proportion of subjects who achieve a PR or CR • Incidence of Grade \geq 4 treatment-emergent adverse events (TEAEs)

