5.3.1. Idelalisib Dose Levels

Idelalisib dose levels are shown in [Table 5-1](#). Subjects will be randomized to Arm A or C. Dose modifications may be made in response to toxicity; see [Table 5-2](#) for dose adjustment rules.

Table 5-1. Idelalisib Dose Levels

Subjects enrolled prior to Protocol Amendment 5:

Dose Level	Dosing Regimen	
	Dose Level 0	150 mg BID
Dose Level -1	100 mg BID	100 mg BID

Subjects enrolled as of Protocol Amendment 5:

Treatment Arm	Starting Dose	Reduced Dose
Arm A	150 mg BID	100 mg BID
Arm C*	150 mg BID	100 mg BID

BID=twice daily

*Arm C: administered in 28-day cycles (21 days on-treatment, 7 days off-treatment)

Consistent with the dose adjustment rules presented in [Table 5-2](#), if a subject experiences an AE that is suspected to be related to idelalisib during the course of study, idelalisib administration should be held, as defined in [Table 5-2](#), until the AE resolves or stabilizes to an acceptable degree. Thereafter, idelalisib may be reinitiated, consistent with the instructions in Section 5.3.2. For any AE that is not included in [Table 5-2](#), reinitiation of idelalisib should be per investigator's discretion.

After an idelalisib dose reduction, the dose need not be re-escalated. However, if the subject tolerates the reduced dose of idelalisib for ≥ 4 weeks, then the dose may be increased back to starting dose at the discretion of the investigator. Such a re-escalation may be particularly warranted if further evaluation reveals that the AE that led to the dose reduction was not related to idelalisib.

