8.7. Pharmacokinetic Analysis

Plasma concentrations of idelalisib/metabolite will be listed and summarized by treatment arm and visit using descriptive statistics (eg, sample size, arithmetic mean, geometric mean, % coefficient of variation, StD, median, minimum, and maximum).

Additionally, a population PK model using a nonlinear mixed-effect modeling technique may be used to characterize the PK of idelalisib and GS-563117. Idelalisib exposure-response relationship between efficacy, safety, and idelalisib and/or GS-563117 exposure may be explored.

A logistic regression model may be used to explore the correlation between drug exposure and efficacy or safety.

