3.1.4. Pharmacokinetics (PK) Analysis Set

The PK Analysis Set includes subjects in the Safety Analysis Set who have received the study drug and have at least 1 sample with detectable drug concentration.

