3.2. Subject Grouping

For analyses based on the ITT Analysis Set, subjects will be grouped according to the treatment to which they were randomized. For analyses based on the Safety Analysis Set, subjects will be grouped according to the actual treatment received. The actual treatment received will differ from the randomized treatment only when their actual treatment differs from randomized treatment for the entire treatment duration.

For the PK Analysis Set, subjects will be grouped according to the actual treatment they received.

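### The PK table is built by arm and visit only, so concentrations at 100 mg and 150 mg are averaged together whenever a subject's dose changes mid-study

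*SAP*

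**What the plan says.** Determining the PK of idelalisib and its metabolite is a secondary objective (SAP 1.1.2), and predose and 1.5-hour idelalisib concentrations are a secondary endpoint (SAP 1.2.2).

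- **Summary rule.** SAP 8: "Plasma concentrations of idelalisib/GS-563117 will be listed and summarized by treatment arm and visit using descriptive statistics". Protocol 8.7 has the same rule: "Plasma concentrations of idelalisib/metabolite will be listed and summarized by treatment arm and visit using descriptive statistics". Neither mentions the dose being taken at the sample.
- **Grouping.** SAP 3.2: "For the PK Analysis Set, subjects will be grouped according to the actual treatment they received". On what counts as a different treatment, the same section says: "The actual treatment received will differ from the randomized treatment only when their actual treatment differs from randomized treatment for the entire treatment duration".
- **Who is included.** SAP 3.1.4 requires dosed subjects to "have at least 1 sample with detectable drug concentration", with no restriction by dose.
- **Dose changes, Arms A and C.** The Protocol Synopsis says for Arm A: "Dose reduction to 100 mg twice daily is available, if required", and for Arm C: "Dose reduction to 100 mg twice daily (21 days on-treatment, 7 days off-treatment) is available, if required". Protocol 5.3.1 also allows a return to the starting dose "if the subject tolerates the reduced dose of idelalisib" for at least 4 weeks.
- **Dose changes, Arm B.** Protocol 3.3 allows subjects randomized to 100 mg who have stable or progressive disease to escalate to 150 mg.
- **Sampling.** Protocol 6.1.5.2 schedules PK at baseline and Weeks 2, 4, 6, 8, 10, 12, 16, 20, 24, 32 and 48.

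**The concern.** A reader of a dose-optimization study will expect the PK table to show what concentrations a given dose and schedule produce. As planned, each cell may be a mixture of two dose levels in proportions that the table does not show. A lower mean at a later visit could come from dose reductions, and a difference between Arms A and C could come partly from different reduction shares and not from the 21/7 schedule. In Arm B the mixing runs upward, because escalated subjects stay in the 100 mg column.

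The by-arm table is also the only PK summary in the SAP. Protocol 8.7 mentions population PK and exposure-response modeling as options, and such modeling could account for dose. SAP 8 does not include it, and SAP 1 gives the SAP precedence over the protocol.

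**Working it through.** The documents state no PK mean, variability or reduction rate, so there is no figure to reproduce. The check has three parts.

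**1. Does any rule separate samples by dose?** No.
- SAP 3.2 assigns subjects, not samples, to groups. Under its entire-duration condition, a mid-study change does not move a subject.
- The PK rules in SAP 3.7 deal with values below the limit of quantitation and log transformation, not with dose.
- Protocol 6.1.5.2 waives the predose sample after a missed or off-treatment dose. It says nothing about a reduced dose.
- SAP 3.8.2 leaves unscheduled visits out of by-visit summaries, so the mixing concerns scheduled samples.

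**2. Which cells can be mixed?** Study day = 7 × week + 1; cycle day = (study day − 1) mod 28 + 1.
- Weeks 2, 6 and 10 are study days 15, 43 and 71, each cycle Day 15.
- Weeks 4, 8, 12, 16, 20, 24, 32 and 48 are study days 29, 57, 85, 113, 141, 169, 225 and 337, each cycle Day 1. In Arm C this directly follows the 7 days off, when the predose sample is not needed.

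On the nominal schedule, Arm C troughs therefore exist only at Weeks 2, 6 and 10 (a reduction before Week 2 is possible in principle). Arm C peaks, and both measures in Arm A, can be mixed up to Week 48. Protocol 1.3 gives median onsets for Grade 3 or higher events of 1.6 months (transaminases), 2 months (rash) and 5 months (diarrhea/colitis). All fall within the sampling period, and Table 5-2 allows resumption at 100 mg after Grade 3 events of each kind.

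**3. How large could it be?** Let f be the share of samples at 100 mg and r the 100/150 mg concentration ratio. Both are assumptions. Relative to the 150 mg value, the pooled arithmetic mean is 1 − f(1 − r) and the geometric mean is r^f. SAP 8 names both statistics.

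| r | f | Arithmetic mean | Geometric mean |
|---|---|---|---|
| 2/3 | 10% | −3.3% | −4.0% |
| 2/3 | 30% | −10.0% | −11.5% |
| 2/3 | 50% | −16.7% | −18.4% |
| 0.8 | 10% | −2.0% | −2.2% |
| 0.8 | 30% | −6.0% | −6.5% |
| 0.8 | 50% | −10.0% | −10.6% |
| 0.9 | 10% | −1.0% | −1.0% |
| 0.9 | 30% | −3.0% | −3.1% |
| 0.9 | 50% | −5.0% | −5.1% |

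For the first row: 1 − 0.1 × (1 − 2/3) = 0.967.

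*Between arms.* Suppose f were 30% in Arm A and 10% in Arm C, with identical concentrations at each dose. The C/A ratio of mean peaks would be 0.967/0.900 = 1.07 at r = 2/3, 0.98/0.94 = 1.04 at r = 0.8, and 0.99/0.97 = 1.02 at r = 0.9. The direction reverses if the shares are reversed.

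*Arm B.* If a share f of samples is at 150 mg and concentration is proportional to dose, the arithmetic mean is multiplied by 1 + 0.5f. It is 10%, 20% or 30% above the 100 mg value for f = 20%, 40% or 60%.

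**The case against.** The strongest reply is that the table answers a legitimate question. Arms A and C are defined as a 150 mg start with a reduction available, so a by-arm mean describes exposure under the regimen as delivered. That stands, and it is why the pooled table should remain. Individual concentrations are listed under SAP 8 and study drug administration under SAP 4.2. However, the items that SAP 4.2 names for its listing do not include dose level, and two separate listings leave the reader to do the linking.

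Three stronger readings are tempting, and the documents do not support them.

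- *The SAP mislabels mixed values as 150 mg values.* SAP 8 labels by arm; it has no 150 mg heading.
- *The Arm A versus Arm C concentration contrast is the basis for judging the 21/7 schedule.* Protocol 1.3 sets the goal as similar efficacy with less toxicity. The primary endpoints are response rate and Grade 4 or higher events. PK is descriptive, SAP 3.5 plans no formal testing, and no comparison of PK between arms is specified.
- *Concentrations will fall over time, and more in the more toxic arm.* No reduction rate is given. Re-escalation is allowed, several toxicities require permanent discontinuation, and Protocol 6 excludes PK sampling after discontinuation. The share at 100 mg need not rise steadily. For Arm C troughs there is no nominal series after Week 10 in which to see a fall.

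Sparse cells are a fair practical objection, since SAP 1 reports early termination for slow enrollment.

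**Conclusion.** The point holds as a limit on what the PK summary can show. Following SAP 8 and SAP 3.2 as written pools two dose levels within an arm and visit, and nothing elsewhere in the plan separates them. The result is exposure under the assigned regimen as delivered, not trough and peak at a dose level, and visit or arm differences cannot be read as effects of schedule alone.

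The size is unknown. The full illustrative range is a fall in the arithmetic mean of 1% to 17% in Arms A and C, for f from 10% to 50% and r from 2/3 to 0.9. Dose proportionality (r = 2/3) is only one of the assumed cases. The extent in Arm C rests on the nominal visit schedule. The change is worth making because it is cheap, but it concerns a descriptive secondary endpoint and does not alter the conclusions on response or Grade 4 or higher events.

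**What to change.** In SAP 8, summarize concentrations by arm (including Arm B), visit, time point (predose, 1.5 hours) and dose being taken at the sample, using the eCRF dosing record. Naming the time point also closes a small gap, since SAP 8 names arm and visit only although the endpoint separates trough from peak. Flag any sample taken during a dose hold, because Protocol 6.1.5.2 makes a predose sample unnecessary after a missed dose but does not rule one out. Keep the pooled by-arm table, with a footnote that it includes all dose levels. Where a cell is too small to summarize, list the values with the dose taken. SAP 1 provides for changes after finalization to be documented in the CSR.

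The cost is one merge of dosing and PK records, extra table dimensions, and some sparse cells given early termination. No new data appear to be needed: Protocol 5.3 has clinic doses recorded with date and time, Protocol 9.1.5 requires the dose regimen in the source record, and Protocol 8.6.1 already plans to report the number and timing of reductions.
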